3.1 STUDY PARAMETERS

3.1.1 Safety Parameters

The safety of acalabrutinib and pembrolizumab will be characterized by the type, frequency, severity, timing of onset, duration, and relationship to study drug(s) of any treatment-emergent AEs or abnormalities of laboratory tests; SAEs; DLTs or AEs leading to discontinuation of study treatment.

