3.8 DOSING DELAYS AND MODIFICATIONS

Subjects should be followed closely for AEs or laboratory abnormalities that might indicate acalabrutinib- or pembrolizumab-related toxicity. If a subject experiences a treatment-related DLT or other intolerable AE during the course of therapy, then acalabrutinib, pembrolizumab, or both drugs should be held, as necessary, until the AE resolves or stabilizes to an acceptable degree. In cases where pembrolizumab is held, pembrolizumab should be restarted in agreement with its original dosing schedule (every 3 weeks). As appropriate, certain laboratory abnormalities may warrant more frequent monitoring (eg, once per week) until abnormalities have recovered to Grade ≤ 1 . Dose reductions for acalabrutinib are provided in [Table 3-2](#). If acalabrutinib is reduced for apparent treatment-related toxicity, the dose need not be re-escalated, even if there is minimal or no toxicity with the reduced dose. However, if the subject tolerates a reduced dose of acalabrutinib for ≥ 4 weeks then the dose may be increased to the next higher dose level, at the discretion of the investigator. Such re-escalation may be particularly warranted if further evaluation reveals that the AE that led to the dose reduction was not treatment-related. However, the maximum dose of acalabrutinib is 100 mg BID for this protocol.

For treatment-emergent hepatotoxicity in the combination arm or for subjects who cross over to receive combination therapy: Important guidelines for treatment-emergent hepatotoxicity are provided in [Section 3.8.2](#) for pembrolizumab. In the combination arm or for subjects who cross over to receive combination therapy, treatment with acalabrutinib should be withheld for Grade 3 or 4 hepatitis. For Grade 4 events, acalabrutinib may be restarted only after discussion with the medical monitor. For Grade 3 events, treatment with acalabrutinib can be considered after the LFT laboratory values have returned to Grade ≤ 1 or to baseline.

Note: Temporary withholding of study drug for as little as 7 days can cause a transient worsening of disease and/or of constitutional symptoms. Refer to [Section 3.12](#) for more information on assessing disease progression under these circumstances.

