3.8.1 Dose Modifications for Pembrolizumab

AEs (nonserious and serious) associated with pembrolizumab exposure may represent an immunologic etiology. These AEs may occur shortly after the first dose or several months after the last dose of treatment. Pembrolizumab must be withheld for drug-related toxicities and severe or life-threatening AEs as per [Table 3-3](#) below. See [Section 3.8.2](#) for supportive care guidelines, including use of corticosteroids.

Table 3-3. Dose Modification Guidelines for Drug-Related Adverse Events

Toxicity	Hold Treatment For Grade	Timing for Restarting Treatment	Treatment Discontinuation
Diarrhea/Colitis	2-3	Toxicity resolves to Grade 0-1.	Toxicity does not resolve within 12 weeks of last dose or inability to reduce corticosteroid to 10 mg or less of prednisone or equivalent per day within 12 weeks.
	4	Permanently discontinue	Permanently discontinue
AST, ALT, or Increased Bilirubin	2	Toxicity resolves to Grade 0-1	Toxicity does not resolve within 12 weeks of last dose.
	3-4	Permanently discontinue (see exception below) ^a	Permanently discontinue
Type 1 diabetes mellitus (if new onset) or Hyperglycemia	T1DM or 3-4	Hold pembrolizumab for new onset Type 1 diabetes mellitus or Grade 3-4 hyperglycemia associated with evidence of beta cell failure.	Resume pembrolizumab when patients are clinically and metabolically stable.
Hypophysitis	2-4	Toxicity resolves to Grade 0-1. Therapy with pembrolizumab can be continued while endocrine replacement therapy is instituted	Toxicity does not resolve within 12 weeks of last dose or inability to reduce corticosteroid to 10 mg or less of prednisone or equivalent per day within 12 weeks.
Hyperthyroidism	3	Toxicity resolves to Grade 0-1	Toxicity does not resolve within 12 weeks of last dose or inability to reduce corticosteroid to 10 mg or less of prednisone or equivalent per day within 12 weeks.
	4	Permanently discontinue	Permanently discontinue
Hypothyroidism		Therapy with pembrolizumab can be continued while thyroid replacement therapy is instituted	Therapy with pembrolizumab can be continued while thyroid replacement therapy is instituted.
Infusion Reaction	2 ^b	Toxicity resolves to Grade 0-1	Permanently discontinue if toxicity develops despite adequate premedication.
	3-4	Permanently discontinue	Permanently discontinue

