Pneumonitis	2	Toxicity resolves to Grade 0-1	Toxicity does not resolve within 12 weeks of last dose or inability to reduce corticosteroid to 10 mg or less of prednisone or equivalent per day within 12 weeks.

Toxicity	Hold Treatment For Grade	Timing for Restarting Treatment	Treatment Discontinuation
	3-4	Permanently discontinue	Permanently discontinue
Renal Failure or Nephritis	2	Toxicity resolves to Grade 0-1	Toxicity does not resolve within 12 weeks of last dose or inability to reduce corticosteroid to 10 mg or less of prednisone or equivalent per day within 12 weeks.
	3-4	Permanently discontinue	Permanently discontinue
All Other Drug-Related Toxicity ^c	3 or Severe	Toxicity resolves to Grade 0-1	Toxicity does not resolve within 12 weeks of last dose or inability to reduce corticosteroid to 10 mg or less of prednisone or equivalent per day within 12 weeks.
	4	Permanently discontinue	Permanently discontinue

Note: Permanently discontinue for any severe or Grade 3 (Grade 2 for pneumonitis) drug-related AE that recurs or any life-threatening event.

a. For patients with liver metastasis who begin treatment with Grade 2 AST or ALT, if AST or ALT increases by greater than or equal to 50% relative to baseline and lasts for at least 1 week then patients should be discontinued.

b. If symptoms resolve within one hour of stopping drug infusion, the infusion may be restarted at 50% of the original infusion rate (e.g., from 100 mL/hr to 50 mL/hr). Otherwise dosing will be held until symptoms resolve and the subject should be premedicated for the next scheduled dose; Refer to [Table 3-4](#) for further management details.

c. Patients with intolerable or persistent Grade 2 drug-related AE may hold study medication at physician discretion. Permanently discontinue study drug for persistent Grade 2 adverse reactions for which treatment with study drug has been held, that do not recover to Grade 0-1 within 12 weeks of the last dose.

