3.12 WITHDRAWAL OF SUBJECTS FROM STUDY TREATMENT

Any subject has the right to withdraw from the study at any time.

- Study treatment should be discontinued in the event of a toxicity lasting > 28 consecutive days, unless reviewed and approved by the medical monitor.
- Any subject who has confirmed objective evidence of cancer progression while receiving acalabrutinib and pembrolizumab should discontinue study treatment.
Note: Study subjects receiving immunotherapies can experience transient immunotherapy-related increases in lesion size (“pseudoprogression”) preceding tumor regression ([Hodi 2010](#)). If there is uncertainty regarding whether there is true cancer progression, the subject may continue study treatment and remain under close observation (eg, evaluated at 4-week intervals) pending confirmation of progression ([Section 3.11](#)). In particular, transient worsening of disease early in therapy or during temporary interruption of study therapy (eg, for drug-related toxicity, surgery, or intercurrent illness) may not indicate cancer progression. In such circumstances, and if medically appropriate, subjects may resume therapy and relevant clinical, laboratory, and/or radiographic assessment can be attempted to document whether tumor control can be maintained or whether cancer progression has occurred.
- Any subject whose medical condition substantially changes after entering the study should be carefully evaluated by the investigator in consultation with the

medical monitor. Such subjects should be withdrawn from study treatment if continuing would place them at risk.

- Any subject who becomes pregnant should be removed from study treatment.
- Any subject who becomes significantly noncompliant with study drug administration, study procedures, or study requirements should be withdrawn from study treatment in circumstances that increase risk or substantially compromise the interpretation of study results.
- The investigator, in consultation with the medical monitor, may withdraw any subject from study treatment, if, in the investigator's opinion, it is not in the subject's best interest to continue.

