Hypothyroidism occurred in 127 (8.1%) of 1567 patients receiving KEYTRUDA in Trials 1, 2, and 6 including Grade 3 (0.1%) hypothyroidism. The median time to onset of hypothyroidism was 3.3 months (range: 5 days to 18.9 months). The median duration was 5.4 months (range: 6 days to 24.3 months). No patients discontinued KEYTRUDA due to hypothyroidism. Hypothyroidism resolved in 24 (19%) of the 127 patients.

NSCLC

Hyperthyroidism occurred in 10 (1.8%) of 550 patients receiving KEYTRUDA in Trial 1, including Grade 2 (0.7%) or Grade 3 (0.3%) hyperthyroidism. The median time to onset was 1.8 months (range: 2 days to 3.4 months), and the median duration was 4.5 months (range: 4 weeks to 7.5 months). No patients discontinued KEYTRUDA due to hyperthyroidism.

Hypothyroidism occurred in 38 (6.9%) of 550 patients receiving KEYTRUDA in Trial 1, including Grade 2 (5.5%) or Grade 3 (0.2%) hypothyroidism. The median time to onset was 4.2 months (range: 20 days to 11.2 months), and the median duration was 5.8 months (range: 11 days to 22.8 months). No patients discontinued KEYTRUDA due to hypothyroidism.

Type 1 Diabetes mellitus

Type 1 diabetes mellitus, including diabetic ketoacidosis, occurred in 3 (0.1%) of 2117 patients with melanoma or NSCLC receiving KEYTRUDA in Trials 1, 2, and 6. Monitor patients for hyperglycemia or other signs and symptoms of diabetes. Administer insulin for type 1 diabetes, and withhold KEYTRUDA and administer anti-hyperglycemics in patients with severe hyperglycemia [see *Dosage and Administration (2.3)* and *Adverse Reactions (6.1)*].

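### Does the 28-day toxicity stop in Section 3.12 conflict with the 12-week and open-ended limits in Table 3-3?

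*Protocol*

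**What the plan says.** Section 3.12 (Withdrawal of Subjects From Study Treatment) gives a general rule: "Study treatment should be discontinued in the event of a toxicity lasting > 28 consecutive days, unless reviewed and approved by the medical monitor". It names no drug, grade or relationship to treatment.

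Section 3.8 (Dosing Delays and Modifications) says that for a treatment-related DLT or other intolerable event, either drug or both "should be held, as necessary, until the AE resolves or stabilizes to an acceptable degree". It gives no time limit. It does point to Section 3.12, but only "for more information on assessing disease progression under these circumstances".

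Table 3-3 in Section 3.8.1 covers pembrolizumab by type of event:

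- In most hold rows the trigger for permanent discontinuation is "Toxicity does not resolve within 12 weeks of last dose", in most of them with a corticosteroid-taper condition as an alternative trigger.
- Footnote c applies the same period to persistent Grade 2 reactions that "do not recover to Grade 0-1 within 12 weeks of the last dose".
- For hypothyroidism the entry is "Therapy with pembrolizumab can be continued while thyroid replacement therapy is instituted", with no time limit.
- The type 1 diabetes/hyperglycemia row also has no time limit; dosing resumes once the patient is stable.
- Several rows require immediate permanent discontinuation, for example Grade 3-4 pneumonitis or nephritis and Grade 4 colitis.

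Section 3.1.1 lists "DLTs or AEs leading to discontinuation of study treatment" among the safety parameters.

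**The concern.** A reader who puts these places side by side sees 28 days in one and 12 weeks, or no limit, in the others, with no statement of which prevails. Table 3-3 mentions neither 28 days nor the medical monitor. A site working from Table 3-3 alone could keep a subject on hold, or on treatment with thyroid replacement, past day 28 without the approval that Section 3.12 asks for. A site working from Section 3.12 might stop at day 29.

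If sites differed in this way, the number of subjects counted as stopping treatment for an adverse event would depend partly on which section each site consulted. Safety is one of the two primary objectives, so this deserved a check.

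**Working it through.** **Inputs**

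- Section 3.12: 28 consecutive days, counted from onset of the toxicity.
- Table 3-3: 12 weeks = 12 × 7 = 84 days, counted from the last dose.
- Section 3.5: pembrolizumab every 3 weeks = 21 days.

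**Which limit is reached first?** Let *s* be the day of onset relative to the last pembrolizumab dose. The Section 3.12 point falls at *s* + 28 and the Table 3-3 limit at 84, so the gap is 84 − (*s* + 28) = 56 − *s*.

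| Onset relative to last dose | 28-day point | 12-week limit | Gap |
|---|---|---|---|
| Same day (*s* = 0) | day 28 | day 84 | 56 days |
| 21 days after (*s* = 21) | day 49 | day 84 | 35 days |
| 7 days before (*s* = −7, illustrative) | day 21 | day 84 | 63 days |

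The last line shows that 56 days is not a ceiling: Section 3.12 names no grade, so a mild event that predates the last dose and then worsens widens the gap. In every case the 28-day point comes first.

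**Can both provisions be obeyed?**

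1. The event resolves by day 28: only Table 3-3 applies.
2. The event lasts longer and the monitor approves: Section 3.12 is satisfied, and the hold may run up to the Table 3-3 limit.
3. The event lasts longer and approval is not given: treatment stops under Section 3.12. Table 3-3 says when pembrolizumab must stop; it does not guarantee 12 weeks.
4. Hypothyroidism: Table 3-3 permits continuation and does not require it. Review at day 28 can confirm it.
5. Rows with immediate permanent discontinuation: no overlap for pembrolizumab.

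No case forces a site to break one provision in order to keep the other. A site that passes day 28 without review has departed from Section 3.12; it has not been given contrary instructions.

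**How often would it arise?** The clearest case is hypothyroidism. In the package insert (Appendix 6), "Hypothyroidism occurred in 38 (6.9%) of 550 patients receiving KEYTRUDA in Trial 1", with a median duration of 5.8 months and a range of 11 days to 22.8 months. Assume these monotherapy rates apply to 2 × 37 = 74 subjects, and that the median is a simple median over the 38 patients:

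- All episodes: 38/550 × 74 = 5.1 subjects.
- Episodes over 28 days: at least half, since the median is far above 28 days, giving 19/550 × 74 = 2.6. At most 37 of 38, since one lasted 11 days, giving 37/550 × 74 = 5.0.

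That is roughly 3 to 5 subjects across both arms. No total for the other rows can be derived. The liver row concerns laboratory AST, ALT or bilirubin increases, for which the insert gives no Grade 2 rate, and the catch-all row and footnote c have no rate at all.

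**What would the analysis lose?** Section 5.4.1 summarises safety descriptively, with no test or threshold on discontinuations. Section 3.12 requires the date and reason for withdrawal to be recorded on the case report form. Under Section 3.0, subjects who stop for a reason other than progression, death, loss to follow-up or withdrawn consent still have tumor assessments until progression or other anticancer therapy. The sample size in Section 5.1 rests on response rates of 40% and 18%, one-sided α = 0.10 and 80% power; the toxicity-stop rule is not an input.

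**The case for a change.** The best case for a change is practical. Staff managing an immune-related event will turn to Table 3-3, which gives no prompt to call the monitor at day 28. The protocol nowhere says that the specific table overrides the general rule, or the reverse. Section 3.12 speaks of study treatment while Table 3-3 mainly concerns pembrolizumab, so in the combination arm it is not spelled out whether one drug or both are meant. Many events outlast 28 days: the package insert gives median durations of 1.2 months for NSCLC pneumonitis and 4.5 months for NSCLC hyperthyroidism. Section 3.10.1 warns that transaminase elevations may be more frequent with the combination. One sentence would settle it.

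The missing link is real, and so is the silence on which drug is meant. But Section 3.12 is the protocol's own section on withdrawal from treatment and binds sites as much as Table 3-3 does. Its approval clause is the means of settling individual cases, including which drug is affected. A cross-reference would write down what a site following the whole protocol already does; it would not alter an estimate or a decision rule.

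**Conclusion.** No change follows. The provisions set different limits but are compatible: a review at 28 days that may allow continuation, and a later or absent limit specific to pembrolizumab. The gap is a missing cross-reference that sites and the medical monitor can fill in conduct. Its reach is modest and only partly knowable: about 3 to 5 of 74 subjects for hypothyroidism, if the monotherapy rates in the package insert carry over, and not derivable for the other rows. Any effect falls on a descriptive count whose reasons are recorded; no consequence for response rate or progression-free survival by arm is shown.

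This rests on two readings: that the monitor can be asked for approval at day 28, and that Table 3-3 gives an outer limit and not an entitlement to 12 weeks. It implies no opinion on which limit is clinically appropriate.

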	
Although acalabrutinib has not demonstrated any dose-limiting toxicities (DLTs) to date, the safety of acalabrutinib in combination with pembrolizumab in this patient population needs to be assessed and standard DLT criteria will be applied to Arm 2 of the study. Therefore an interim safety analysis will occur once 6 subjects have been successfully randomized to the combination arm (Arm 2) and have been treated a minimum of 4 weeks. Enrollment will be paused while the interim safety analysis occurs. If a DLT rate of < 33% is observed in Arm 2 (ie, DLT review is cleared), then randomization will continue to evaluate the objective response rates of pembrolizumab monotherapy and the combination of pembrolizumab and acalabrutinib (ie, up to 37 total subjects per arm). If a DLT rate of $\geq 33\%$ is observed in Arm 2, then enrollment (1:1) will continue until an additional 6 subjects are randomized to Arm 2, but with a reduced dose level for acalabrutinib (Level -1). If the DLT review is cleared in those additional 6 subjects in Arm 2 then continued enrollment will occur at Level -1 for the combination arm. If a DLT rate of $\geq 33\%$ is observed in Arm 2 at Level -1, then an additional 6 subjects will be randomized at Level -2 and assessed for DLTs. If the DLT review is cleared, continued enrollment will occur at Level -2 for the combination arm. If the DLT review is not cleared, enrollment will be halted in Arm 2.
 
Acalabrutinib treatment can continue for subjects who are tolerating therapy and not progressing. Pembrolizumab treatment is for 24 months from the date of first dose for subjects who are tolerating therapy and not progressing. Subjects who have confirmed progressive disease on the combination of pembrolizumab and acalabrutinib will discontinue study treatment while those with confirmed progressive disease in the pembrolizumab monotherapy arm will continue on pembrolizumab with the addition of acalabrutinib until a second disease progression or intolerance to therapy. For subjects who cross over to receive combination treatment, acalabrutinib treatment will begin at the next visit at which subjects are scheduled to receive pembrolizumab. The immune-related response criteria (irRECIST; Appendix 8) will be used to determine progression on this study. Pembrolizumab treatment can end for subjects with confirmed complete response (CR) if treatment has been administered for at least 24 weeks and 2 doses of pembrolizumab have been administered after confirmation of CR.
 
Refer to Appendix 4 and Appendix 5 for comprehensive lists of study assessments and their timing. A study schema is provided in Figure 3-1.

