4.2 INVESTIGATOR'S ASSESSMENT OF RESPONSE TO TREATMENT

Responses will be categorized as CR, PR, SD, or PD. The definitions of response in target lesions are provided in [Table 4-1](#). The definitions of response in nontarget lesions are provided in [Table 4-2](#).

Table 4-1. Evaluation of Target Lesions (RECIST)

Response Category	Definition
CR	Disappearance of all target and nontarget lesions including normalization of an elevated tumor marker level. Any pathological lymph nodes (whether target or nontarget) must have reduction in short axis to <10 mm.
PR	A $\geq 30\%$ decrease in the sum of the diameters of target lesions taking as a reference the baseline sum of the diameters.
SD	Neither sufficient shrinkage to qualify for PR nor sufficient increase to qualify for PD taking as reference the smallest sum diameters while on study.
PD ^a	At least a 20% increase in the sum of diameters of target lesions, taking as reference the smallest sum on study (this includes the baseline sum if that is the smallest on study). In addition to the relative increase of 20%, the sum must also demonstrate an absolute increase of at least 5 mm. (Note: the appearance of one or more new lesions is also considered progression).

Abbreviations: CR=complete response, PD=progressive disease, PR=partial response, SD=stable disease

- a. Transient apparent worsening of disease early in therapy or during temporary interruption of study therapy (eg, for drug-related toxicity or intercurrent illness) may not indicate true cancer progression. Refer to [Section 3.11](#) for more detailed information.

Evaluation of nontarget lesions: while some nontarget lesions may actually be measurable, they need not be measured and instead should be assessed only qualitatively at the timepoints specified in the Schedule of Assessments.

Table 4-2. Evaluation of Nontarget Lesions (RECIST)

Response Category	Definition
CR	Disappearance of all non-target lesions and normalization of tumor marker level. All lymph nodes must be non-pathological in size (< 10mm short axis).
Non-CR/Non-PD	Persistence of one or more non-target lesion(s) and/or maintenance of tumor marker level above the normal limits.
PD ^a	Uequivocal progression ^b of existing non-target lesions. (Note: the appearance of one or more new lesions is also considered progression).

Abbreviations: CR = complete response; PD =progressive disease.

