5.0 STATISTICAL METHODS OF ANALYSIS

5.1 GENERAL CONSIDERATIONS

Descriptive statistics (including means, standard deviations, and medians for continuous variables and proportions and confidence intervals [CIs] for discrete variables) will be used to summarize data as appropriate.

For the interim safety analysis (DLT review), enrollment of 6 subjects in the combination arm for DLT review is consistent with sample sizes used in oncology studies for determination of MTD. The trial employs the standard National Cancer Institute definition of MTD (dose associated with DLT in $\leq 17\%$ of subjects). Provided the DLT review period is cleared in the combination arm and this arm is not stopped early for futility or toxicity ([Section 5.5](#)), then up to 31 subjects will be added per arm.

The sample size for this 2-arm trial was determined by a Z-test for normal approximation of binomial distribution, based on one-sided $\alpha = 0.10$, 80% power, with projected response rates of 40% in pembrolizumab/acalabrutinib arm and 18% in pembrolizumab

arm. [REDACTED] PASS version 11 was employed to conduct the sample size calculation.

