12.3 Pharmacokinetics

The pharmacokinetics of pembrolizumab was studied in 2195 patients who received doses of 1 to 10 mg/kg every 2 weeks or 2 to 10 mg/kg every 3 weeks. Based on population pharmacokinetic analyses

in patients with solid tumors, the geometric mean [% coefficient of variation (CV%)] for clearance, steady-state volume of distribution, and terminal half-life were 202 mL/day (37%), 7.38 L (19%) and 27 days (38%), respectively.

Steady-state concentrations of pembrolizumab were reached by 19 weeks of repeated dosing with an every 3-week regimen and the systemic accumulation was 2.2-fold. The peak concentration (C_{\max}), trough concentration (C_{\min}), and area under the plasma concentration versus time curve at steady state (AUC_{ss}) of pembrolizumab increased dose proportionally in the dose range of 2 to 10 mg/kg every 3 weeks.

Specific Populations: The effects of various covariates on the pharmacokinetics of pembrolizumab were assessed in population pharmacokinetic analyses. The CL of pembrolizumab increased with increasing body weight; the resulting exposure differences were adequately addressed by the administration of a weight-based dose. The following factors had no clinically important effect on the CL of pembrolizumab: age (range: 15 to 94 years), gender, race, renal impairment, mild hepatic impairment, or tumor burden.

Renal Impairment: The effect of renal impairment on the CL of pembrolizumab was evaluated by population pharmacokinetic analyses in patients with various solid tumors and mild (eGFR 60 to 89 mL/min/1.73 m²; n=937), moderate (eGFR 30 to 59 mL/min/1.73 m²; n=201), or severe (eGFR 15 to 29 mL/min/1.73 m²; n=4) renal impairment compared to patients with normal (eGFR greater than or equal to 90 mL/min/1.73 m²; n=1027) renal function. No clinically important differences in the CL of pembrolizumab were found between patients with renal impairment and patients with normal renal function [see *Use in Specific Populations* (8.6)].

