4.3.1. Evaluation of target lesions

Complete Response (CR): Disappearance of all target lesions.

Any pathological lymph nodes (whether target or non target) must have reduction in short axis to <10 mm.

Partial Response (PR): At least a 30% decrease in the sum of diameters of target lesions, taking as reference the baseline sum diameters.

Progressive Disease (PD): At least a 20% increase in the sum of diameters of target lesions, taking as reference the smallest sum on study (this includes the baseline sum if that is the smallest on study). In addition to the relative increase of 20%, the sum must also demonstrate an absolute increase of at least 5 mm. (Note: the appearance of one or more new lesions is also considered progression).

Stable Disease (SD): Neither sufficient shrinkage to qualify for PR nor sufficient increase to qualify for PD, taking as reference the smallest sum diameters while on study.

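### Footnote a to RECIST Tables 4-1 and 4-2 lets an unblinded investigator set aside progression seen during a drug hold, with no limit or dating rule, and Arm 2 has more occasions to use it

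*Protocol*

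**What the plan says.** The interruption caveat appears in three places.

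- Section 3.8: "Temporary withholding of study drug for as little as 7 days can cause a transient worsening of disease and/or of constitutional symptoms". The reader is sent to Section 3.12 for how to assess progression in that situation.
- Section 3.12, on withdrawal from treatment: "transient worsening of disease early in therapy or during temporary interruption of study therapy" may not be cancer progression, and therapy may resume while progression is documented.
- Section 4.2, footnote a on the PD row of both Table 4-1 (target lesions) and Table 4-2 (nontarget lesions): "Transient apparent worsening of disease early in therapy or during temporary interruption of study therapy" may not be true progression. This time the reader is sent to Section 3.11.

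Section 5.4.4 takes ORR and DCR from Section 4.2, names ORR by RECIST as the primary endpoint, and evaluates irRECIST additionally. PFS and DOR end at documented progression or death. Section 4.2.2 collects best overall response from the start of treatment up to progression.

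Appendix 7 (RECIST 1.1, Section 4.3.1) defines PD by measurement: "At least a 20% increase in the sum of diameters of target lesions, taking as reference the smallest sum on study", with an absolute increase of at least 5 mm. It makes no exception for a drug hold.

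**The concern.** A statement that worsening off drug may be transient does no harm as advice on whether to continue treatment. As a footnote to the RECIST PD rows it becomes part of the endpoint definition. It depends on an event after randomisation (a hold) and is applied by an investigator who knows the arm. The consequences of the call also differ by arm: confirmed progression ends treatment in Arm 2 and can open crossover in Arm 1.

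At stake are the date of progression (PFS, DOR) and the period in which a response may still be counted (ORR). If holds coincide with scans more often in one arm, the same tumour measurements can be scored differently in the two arms.

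**Working it through.** **1. The plan's own figure.** Section 5.1 sizes the trial for "80% power, with projected response rates of 40% in pembrolizumab/acalabrutinib arm and 18% in pembrolizumab" arm, one-sided alpha 0.10. With unpooled variance,

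n = (z0.90 + z0.80)² × [p1(1−p1) + p2(1−p2)] / (p1−p2)² = 4.508 × (0.2400 + 0.1476) / 0.0484 = 36.1, rounded up to 37.

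This matches "up to 37 total subjects per arm" in the Synopsis. The pooled form gives 38. Power at 37 is 80.7% (unpooled) or 79.6% (pooled). I use 37 per arm below.

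**2. Is there an operating rule?** Section 3.8 names 7 days as enough to cause worsening and points to 3.12. Section 3.12 says only that reassessment can be attempted. The footnotes point to 3.11, which calls for a repeat scan at 4 weeks or later after any first radiologic progression but has no rule for interruptions. None of these gives a minimum or maximum hold, or the progression date if worsening during a hold is later confirmed. By contrast, Appendix 7 Section 4.4.4 dates equivocal progression that is later confirmed at the earlier scan.

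**3. Opportunity by arm.**

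| Source of a hold | Arm 1 | Arm 2 |
|---|---|---|
| Pembrolizumab toxicity (Table 3-3) | yes | yes |
| Acalabrutinib for Grade 3-4 hepatitis (3.8) | only after crossover | yes |
| Acalabrutinib around major surgery (3.10.5) | only after crossover | yes |
| More transaminase elevation on the combination (3.10.1) | only after crossover | yes |

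A 7-day hold is also hard to define for a drug infused every 3 weeks. The package insert (Appendix 6, Section 12.3) gives clearance, volume and half-life as "202 mL/day (37%), 7.38 L (19%) and 27 days (38%), respectively", so the half-life is 27 days. The Section 3.12 bullet carrying the note is worded for subjects on both drugs. More use in Arm 2 is therefore a reasonable inference, but no hold rates are given.

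**4. PFS, by simulation.** Inputs from the protocol: 37 per arm; scans at Weeks 7, 13 and 19, then every 12 weeks. Assumptions: no true difference, exponential progression with median 3-6 months, and the share of first progressions discounted in each arm.

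| Share discounted, Arm 2 v Arm 1 | Dated at next scheduled scan | Dated at 4-week repeat scan | Back-dated to first scan |
|---|---|---|---|
| 20-30% v 5% | HR 0.86-0.95 | HR 0.96-1.00 | no shift |
| 10% v 2% | HR 0.94-0.98 | HR about 1.00 | no shift |

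**5. Primary ORR, by exact binomial enumeration.** Pooled Z-test at one-sided 0.10, 37 per arm, true ORR 18% in both arms. The clause adds d expected counted responders in Arm 2, so the Arm 2 rate becomes 0.18 + d/37 (for d = 1, 0.207). The documents give no value for d.

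| d | Arm 2 only | Arm 1 gains half as many | Both arms gain d |
|---|---|---|---|
| 0 | 0.099 | 0.099 | 0.099 |
| 1 | 0.162 | 0.129 | 0.102 |
| 2 | 0.242 | 0.163 | 0.105 |
| 3 | 0.337 | 0.199 | 0.106 |
| 4 | 0.440 | 0.236 | 0.104 |

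Entries are the probability of a false-positive comparison. Any harm comes from asymmetry between arms; equal use leaves the error near 0.10.

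**The case against.** The strongest reply is that the clause is arm-neutral. It covers early therapy, intercurrent illness and surgery, and Table 3-3 holds pembrolizumab in both arms. Section 3.11 already lets a first radiologic progression be rechecked in either arm, hold or no hold, so the extra room given by the interruption wording may be small. Adapting RECIST is a declared choice, so the lack of an exemption in Appendix 7 is not in itself a contradiction. Detailed censoring rules are left to the SAP.

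Much of this stands. A reader might infer that Arm 2 is scored more leniently, or that the clause is available mainly to Arm 2. The documents do not support that: the wording is permissive, it names no arm, and no frequency is stated.

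A reader might also take the lower hazard ratios as the expected bias. They rest on assumed discount rates and on dating at the next scheduled scan, whereas Section 3.11 provides for a repeat scan from 4 weeks. Nor would a log-rank rejection rate be the error of any stated analysis, since Section 5.4.4 gives only Kaplan-Meier estimation for PFS.

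For ORR, an extra responder must meet PD, have it discounted, then shrink by at least 30% from baseline and have that confirmed (Table 4-4). This may be rare.

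The SAP argument does not remove the point. What is deferred is how surviving, non-progressing subjects are censored, not what counts as PD. Nontarget PD is a qualitative call; if the investigator does not record it, measurements cannot restore it later. And Section 5.4.4 already provides irRECIST as the separate place for immune-related flexibility.

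**Conclusion.** The point holds in a limited form. An undefined discount sits on the RECIST PD definition in an open-label, investigator-assessed trial, the cross-references disagree, and Arm 2 has more occasions to invoke the interruption part. PFS, DOR and, through the best-response window, the primary ORR can therefore be scored differently by arm; the documents do not show that they would be.

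The size cannot be derived from the protocol. For PFS it depends more on how a discounted progression is dated, which the footnote leaves open, than on the assumed rates: it ranges from nothing (back-dating) to a hazard ratio near 0.86 in the least favourable case examined. For ORR, one net extra expected responder in Arm 2 would raise a nominal 0.10 error to about 0.16, but whether there would be even one is unknown.

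**What to change.** For the RECIST 1.1 endpoints (ORR, DCR, DOR, PFS):

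- Remove the interruption wording from footnote a of Tables 4-1 and 4-2.
- State that in both arms every scan is scored as measured whether or not drug is on hold, and that PD is dated at the first scan meeting RECIST 1.1.
- Keep immune-related flexibility in the separate irRECIST analyses.
- State in Section 3.12 that its interruption note concerns only whether treatment continues. Treatment decisions themselves are left as they are.
- Reconcile the references among Sections 3.8, 3.11, 3.12 and 4.2.

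The cost is wording only. PFS, and possibly ORR, may look slightly less favourable, because worsening that later reverses would count as progression under RECIST 1.1. The irRECIST results would show how much that matters.
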